4. BASIC STUDY DESIGN

APPROACH

Overview of Study Design

The goal of the project is to increase both patient and organizational readiness to address trauma and CVD risk among PLWHIV in two healthcare organizations in Los Angeles County. These organizations have indicated their strong interest in being able to meet CVD-related needs of their HIV-positive clients and their capacity to do so, with training and support (see Letters of Support). Using an effectiveness/implementation hybrid research design,¹⁵ this study will investigate: (1) organizational factors associated with implementation outcomes⁷⁶ (adoption, guideline adherence, feasibility, sustainability); and (2) effectiveness of the intervention as delivered to 260 PLWHIV receiving care in the two participating organizations. For purposes of this study, the investigators operationalize “successful implementation”⁷⁶ as a combination of number of individuals served (approximately 130 individuals per agency), a minimum of 12 completed cycles of the five-week intervention, delivery of the intervention with fidelity and documentation of adaptations, and high level of satisfaction with the intervention. The investigators will also study maintenance and evolution of the intervention, i.e., whether the participating organizations continue to offer HHMB and CVD-related services after the active implementation period.

To achieve our implementation aims (Aims 1 & 2), a mixed methods evaluation will be conducted throughout each REP phase, as detailed below. Staff and organizational characteristics will be assessed in Year 1, and engagement and training will be priorities. Following successful training, implementation will commence in both organizations in the first year. After a 26-month implementation phase, maintenance and evolution will be studied for six months, during which time only technical assistance will be provided. For our intervention effectiveness aim (Aim 3), the investigators will use an intra-change within subjects (pre/post change) design.

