In addition to these structured measures, key stakeholders who provide written consent will complete semi-structured interviews. These interviews will be conducted with a subset of key stakeholders who will be directly involved in implementation (n~5/agency). *Pre-conditions phase interviews* will focus on perceived barriers and facilitators to implementation, familiarity with CVD and trauma among PLWHIV, and suggestions for education and other implementation strategies that the investigators intend to use. *Mid-implementation interviews* will include questions about feasibility, satisfaction, perceived fidelity, barriers, desired revisions, and expectations for maintenance and evolution. *Maintenance phase interviews* will include similar questions but will refer to the maintenance phase and stakeholders' satisfaction with and future expectations of the utility of HHMB as a long-term option for agencies' usual menu of services.

Organizational Implementation Evaluation

Several types of assessments will be used to track implementation processes, specifically with regard to fidelity, dose, and intensity of intervention. Throughout the intervention, the investigators will monitor: session attendance, session completion, and participant satisfaction with sessions. Facilitators/navigators will also complete short surveys noting adherence to the curriculum, level of participation, specific obstacles that may have arisen, and what components appeared to be most/least appropriate for the session's participants. Facilitators will also complete overall ratings of each participant's engagement, competency, and knowledge. To assess fidelity, sessions will be digitally recorded. For the first intervention cohort at each site, all recordings will be reviewed by [name] and feedback will be provided to facilitators/navigators. Subsequently, a random 15% sample of all session recordings will be reviewed and scored for fidelity to core elements, with a criterion of 80% or more of the total elements considered acceptable.¹⁰⁸

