Specific Aim 2. To evaluate the use and effectiveness of implementation strategies over time, and identify barriers and facilitators to organizational adoption of guidelines, provider adherence to guidelines, feasibility, and sustainability, the investigators will draw on the Consolidated Framework for Implementation Research (CFIR),¹⁸ which provides an analytic rubric for examining intervention and provider characteristics, as well as inner and outer settings. Data regarding acceptability, barriers, and facilitators will be derived from interviews and implementation-focused evaluation measures. As the investigators are examining implementation in two large healthcare organizations, barriers and facilitators will likely vary by agency. Descriptive statistics will be used to analyze the survey data, given the small sample size and the modest, practical goal of characterizing the agencies in preparation for implementation. In addition, the investigators will examine the facilitator/navigator and participant satisfaction ratings to characterize acceptability of the intervention. These ratings will be compared both within and across cohorts and organizations. Potential determinants of adoption and fidelity include but are not limited to training factors, competency at delivering the intervention, types of facilitators/navigators, participant “mix” (including gender and racial/ethnic diversity) in a given cohort, retention, and satisfaction. All of these factors will be examined when characterizing fidelity across agencies. In addition, based on interviews with facilitators/navigators and clients, the investigators will remain open to other determinants that may emerge during implementation. There are several possible determinants of maintenance. The investigators hypothesize that sustainability will be achieved in agencies that have their own trained staff facilitators who deliver the intervention with fidelity and who had positive experiences with the intervention during the implementation phase.

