Qualitative data analysis: All interviews will be digitally recorded and transcribed by a professional transcription company. Analysis will be conducted primarily by [name] and [name] (who has been trained by [name]), utilizing ATLAS.ti, a software package that allows for fluid “interaction” of data types and sources. Using constant comparison analytic methods,¹¹⁰ a preliminary codebook will be developed both deductively using CFIR and inductively from a sub-sample of interviews within and across organizations at baseline. Qualitative findings at baseline will be augmented by preliminary analyses of staff-level data from the structured measures described above (e.g., burnout, organizational climate, etc.), and a baseline profile will be developed for each agency. These profiles will be reviewed by the Implementation Team, and will be used to tailor implementation strategies at each site (e.g., where there is a high level of burnout, additional attention will be paid to supporting staff and managing workload throughout implementation). This approach of using baseline data as diagnostic and informative for tailored implementation has been employed by [name] in a prior implementation study.¹¹¹ The codebook will be elaborated upon and adjusted as each round of interviews is reviewed until thematic saturation is achieved within and across cycles of interviews. Interviews will be compared within each organization, across organizations, across different types of respondents, and over time. Additional sources of qualitative data (i.e. meeting minutes, monthly reflections, archival information) will also be included in the data set. The investigators will analyze the data specifically for barriers to and facilitators of implementation, including but not limited to the ways in which the project’s implementation strategies affect adoption, fidelity, and sustainability. In addition to identifying themes and patterns qualitatively, the investigators will examine statistical associations between important process and outcome variables such as satisfaction with the intervention, fidelity, and retention, and improvement in behavioral outcomes. Agency profiles will be revisited and further developed at the end of the active implementation phase, and again after implementation, thereby creating a story of implementation at each organization.

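### Spread the 15% fidelity sample over sites and cohorts: if the draw is unstratified, about 35–45% of cohorts after the first at each site would have no independently scored session (assuming 5 sessions per cycle)

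*Combined protocol and SAP*

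**What the plan says.** Section 9 (Organizational Implementation Evaluation) has all sessions recorded and treats early and later cohorts differently. "For the first intervention cohort at each site, all recordings will be reviewed by" a study team member, with feedback to the facilitators. After that, "a random 15% sample of all session recordings will be reviewed and scored for fidelity to core elements". A score passes if at least 80% of the elements were delivered. The selection is called random and nothing more is said about how it is made. The same section has facilitators/navigators complete short surveys on their own adherence to the curriculum.

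Fidelity scores have three uses:

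- Section 4 includes "delivery of the intervention with fidelity and documentation of adaptations" in its definition of successful implementation, next to "a minimum of 12 completed cycles of the five-week intervention".
- Section 14.1, Specific Aim 2, lists possible determinants of adoption and fidelity, among them the gender and racial/ethnic make-up of each cohort, retention and satisfaction. It then says: "All of these factors will be examined when characterizing fidelity across agencies".
- Section 14.1, Qualitative data analysis, plans to examine "statistical associations between important process and outcome variables such as satisfaction with the intervention, fidelity, and retention, and improvement in behavioral outcomes".

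**The concern.** The intervention is delivered to groups in cycles. Cohort composition is a cohort-level variable, so studying it as a determinant of fidelity needs a fidelity value for each cohort. In the same way, a client can be linked to observed fidelity only through the sessions of his or her own cohort. Section 15.1 plans one facilitator/navigator per organization, so a fidelity value held only at facilitator or agency level would take little more than two values and could not be separated from site.

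An unstratified draw leaves the spread over cohorts to chance: some cohorts get two or three scored sessions and others none. For a cohort with none, the two analyses above would have to omit its clients or fall back on the facilitator's own report.

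**Working it through.** The plan gives no coverage figure, so there is none to reproduce. The check asks how many cohorts an unstratified 15% draw would miss.

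**Inputs from the documents**
- Sampling fraction 15%, applied after the first cohort at each site (section 9).
- Two sites (section 4: "effectiveness of the intervention as delivered to 260 PLWHIV receiving care in the two participating organizations").
- At least 12 cycles (section 4). Whether this is a total or per agency is not stated, so both are computed: 12 or 24 cohorts, hence 12 − 2 = 10 or 24 − 2 = 22 later cohorts.

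**Assumptions**
- Sessions per cycle, s: not stated. Section 4 gives only a five-week length. Base case s = 5 (one per week), range 4 to 10.
- The draw is unstratified.
- The cycle count is exactly the stated minimum.

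**Formula.** With M later sessions and n of them drawn without replacement, P(a given cohort has no scored session) = C(M − s, n) / C(M, n). Expected unscored cohorts = later cohorts × P.

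**Base case, s = 5**
- 12 cycles in total: M = 10 × 5 = 50, and 15% is 7.5.
  - n = 8: C(45,8)/C(50,8) = 0.401, or 4.0 of 10.
  - n = 7: 0.454, or 4.5 of 10.
  - If the 15% is counted on all 60 sessions but drawn from the later 50, n = 9: 0.354, or 3.5 of 10.
- 12 cycles per agency: M = 22 × 5 = 110, and 15% is 16.5.
  - n = 17: 0.425, or 9.3 of 22.
  - n = 16: 0.448, or 9.9 of 22.
- Rough check, treating selections as independent: 0.85^5 = 0.444.
- Simulation of the 50/8 case (200,000 draws): 3 to 5 of the 10 later cohorts unscored in 93% of draws. The gap is the usual result, not an unlucky one.

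**As a share of all cohorts.** Counting the first cohorts as scored, 4.0/12 = 33% (n = 8) or 9.3/24 = 39% (n = 17). Section 9 says that first-cohort recordings are reviewed; it does not expressly say that they are scored.

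**Sensitivity to sessions per cycle** (12 cycles in total, n = 15% of later sessions, rounded up). The last column takes the same n with at most one session per cohort until all are covered, so it equals max(0, 10 − n).

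| s | M | n | P unscored | Unscored, unstratified | Unscored, stratified |
|---|---|---|---|---|---|
| 4 | 40 | 6 | 0.507 | 5.1 of 10 | 4 of 10 |
| 5 | 50 | 8 | 0.401 | 4.0 of 10 | 2 of 10 |
| 6 | 60 | 9 | 0.360 | 3.6 of 10 | 1 of 10 |
| 8 | 80 | 12 | 0.255 | 2.5 of 10 | 0 of 10 |
| 10 | 100 | 15 | 0.181 | 1.8 of 10 | 0 of 10 |

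At s = 5 with rounding down, stratifying leaves 10 − 7 = 3 of 10. With 22 later cohorts it leaves 22 − 17 = 5 or 22 − 16 = 6. Since 15% of 5 is 0.75 sessions per cohort, full coverage needs one in five, or 20%.

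**Agency level** (50/8 case, 25 later sessions per site). Each site has at least 2 scored sessions in 95% of draws and a site has none in 0.4%. The average is 8/2 = 4 per site.

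**The case against.** The strongest reply is that the plan's stated comparison is of fidelity across agencies, and at that level the draw works: both sites are almost always represented. The sentence in Specific Aim 2 about comparing within and across cohorts concerns satisfaction ratings, not fidelity scores. This stands. A reader might infer that the planned fidelity comparisons as a whole have no data behind them; the documents do not support that. Nor do they support saying that the success criterion in section 4 is compromised, because a random sample estimates overall fidelity without bias.

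It is also true that unscored cohorts are not without any fidelity information. Facilitator adherence surveys are not limited to the 15% sample. They are self-report by the people being assessed, so they supplement scored recordings and do not replace them.

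Next, the text says only random. It neither commits to a simple random draw nor rules out stratification. So the percentages describe what follows if nothing further is done, not a stated intention.

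Finally, the association of fidelity with outcomes is one exploratory clause with no model specified, and a few more scored cohorts will not make it precise. That is a fair reason to rate the point low. It is not a reason to prefer a draw that covers fewer cohorts for the same effort.

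**Conclusion.** The point holds as a minor design improvement. With 5 sessions per cycle and an unstratified draw, about 35–45% of cohorts after the first at each site would have no independent fidelity score. The range is about 18% to 51% for 10 down to 4 sessions per cycle, and the figure is about a third or somewhat more if first cohorts count as scored. The result rests on the unstated number of sessions, on the reading of the 12-cycle minimum and on the absence of stratification.

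The effect is confined to two analyses: cohort composition as a determinant of fidelity, and fidelity against behavioral outcomes. In both, many cohorts would lack an independent score.

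A reader might also infer that stratifying at 15% solves the problem. At 5 sessions per cycle it does not. It about halves the gap when the sample is rounded up (40% to 20%, or 42% to 23%) and does less when rounded down (45% to 30%, or 45% to 27%). Each covered cohort then rests mostly on a single session.

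**What to change.** In section 9, replace the unspecified random draw with a random sample stratified by site and cohort. Take one randomly chosen session from each cohort before taking a second from any, balance the choices over session number, and keep the total at 15%. Where the total is smaller than the number of cohorts, choose the cohorts to be scored at random within site. With equal numbers of sessions per cohort and the same fraction at each site, the overall fidelity estimate stays unbiased; otherwise weight by the selection probability. State the number of sessions per cycle and whether the 12 cycles are a total or per agency.

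Cost: no additional review, only a selection list.

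Optionally, set the sample at one recording per cohort (20% at 5 sessions per cycle). This covers every later cohort for 10 − 8 = 2 or 10 − 7 = 3 more reviews, or 22 − 17 = 5 or 22 − 16 = 6, over the whole study. It is also easier to run, because the session can be picked when each cohort starts. One session remains a noisy measure of a cohort, and the analysis should say so.

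If neither change is wanted, section 14.1 should say that scored fidelity will be analysed at agency level only.

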10. MEDICATION ADHERENCE

The investigators will obtain self-report of adherence to medications.

11. COST CONSIDERATIONS

Not applicable.

12. OUTCOME DETERMINATIONS

12.1 Primary Endpoints

As described above (§8 & 9), client-level outcomes will be assessed with regard to change in psychological symptoms (depression, post-traumatic stress, anxiety, emotional regulation) and cardiovascular health (e.g., sleep, BMI, smoking, physical activity, diet).

12.2 Secondary Endpoints

The investigators will also measure covariates that may influence intervention outcomes, such as adherence to HIV and CVD medications and satisfaction with the intervention.

13. PARTICIPANT SAFETY AND ADVERSE EVENTS

13.1 Institutional Review Board

All procedures are being reviewed by the UCLA Institutional Review Board, which will also serve as the IRB of record for the participating agencies. The study is divided into phases for review, with Phase 1 (slated for approval in October 2018) comprised of data collection at the organizational level, and Phase 2 (to be submitted as a modification in October 2018, following Phase 1 approval) comprised of data collection at the patient-level.

13.2 Informed Consent

All participants, both agency staff and clients, will have the capacity to give informed consent. The Principal Investigators, Co-investigators, HHMB Facilitators/Navigators, Agency PIs, and Project Coordinator will invite individuals to participate, discuss the study procedures and their rights and responsibilities as participants. Each prospective participant will be given the opportunity to ask questions. They will be asked to summarize their understanding of the purpose and procedures of the study. Individuals will then be asked to sign a consent form, and will be given a copy for their records. No information about the research purpose and design will be withheld from participants. Clients will not be denied HIV-related services regardless of their participation. Staff employment will not be affected by decision to participate.

13.3 Voluntary Withdrawal from the Study

Participation in this study is completely voluntary for both agency personnel and clients. Participants will be informed that they have the right to refuse to be in the study or to answer any question that they do not choose to. If they decide not to participate, they can drop out at any time without losing any benefits to which they are otherwise entitled and they will be reimbursed for their time and participation, as described above. Participants will not waive any legal claims, rights or remedies because of their withdrawal from participation in this study.

13.4. Adherence Assessments

The investigators will use the Morisky scale and the HIV adherence questions to assess adherence.

13.5. Summary of the Risks and Benefits

Potential Risks and Risk Estimate

For agency staff respondents, the most important risk is disclosure of their responses on the organizational survey and in the interviews, and any potential consequences to their employment if this were to occur. However, this risk is considered minimal because the focus of the implementation evaluation is not on the person him/herself, but rather on perceptions of the organization's readiness. Implementation climate, leadership, and the HHMB intervention. Nevertheless, several precautions will be used to ensure the confidentiality of the responses, including assigning each participating staff member a research ID number, and having them complete the agency-level measures online on a password-protected study website where their responses are only accessible to the project management team at UCLA. Also, all data will be analyzed and reported in the aggregate, with no identification of individuals or agencies. Agency leadership will not have access to their staff's data under any circumstances.

In a study of disease prevention, ethical issues that impact human participants' protection are of primary importance. The physical, psychological and medical well-being of all participants enrolled in this project is of ultimate concern. The research procedures have been designed to protect participants, respect their right to confidential participation, and ensure their safety at all times. In so doing, regardless of whether issues emerge during the orientation to the study, the ACASI administration of the pre- or post-test, or group sessions, participants can take breaks as necessary, be provided with refreshments, and will be encouraged to ask questions or request clarification of any information that they are unsure of. Despite these precautions,

participation in this study involves a number of risks. Although unlikely, breach of confidentiality regarding HIV serostatus and/or trauma histories may cause participants some level of psychological, social or financial distress. Participant HIV serostatus will be kept strictly confidential and known only to the group in which s/he is participating (as all participants will be HIV-positive). Participants are also likely to experience some distress or embarrassment when responding to some of the questions in the assessment, although this is minimized considerably by using the ACASI methodology, which allows participants to respond to sensitive questions in complete privacy. Participants are also likely to feel some discomfort divulging personal information in the group sessions, especially initially. However, the groups will be led by trained facilitators/navigators who will be sensitive to helping participants to moderate this discomfort.

Potential Benefits of Participation

The potential benefits to agency staff who participate in the study are substantial. The agency staff who participates in the training will gain invaluable information and skills that can be utilized in other areas of their careers. The agency's capacity to properly implement this intervention at their agency will be increased. They will also gain capacity to address CVD risk among their HIV-positive clients. Client participants are likely to gain information and skills that can help them live healthier and more fulfilling lives. They may also increase their support networks by meeting others who may have similar CVD risks and/or trauma histories, are affected and infected by HIV, or have other life challenges. In addition, there are several potential benefits of this research to the field and to society with the generation of evidence about the effectiveness of a feasible, flexible intervention targeting multiple co-occurring conditions, as well as evidence about implementation strategies that can support agencies in enhancing their services to address co-morbid health issues.

